14	DATA HANDLING AND RECORD KEEPING.....	20
14.1	DATA COLLECTION AND MANAGEMENT RESPONSIBILITIES.....	20
14.2	STUDY RECORDS RETENTION.....	21
14.3	PROTOCOL DEVIATIONS	21
14.4	PUBLICATION AND DATA SHARING POLICY	21
15	STUDY FINANCES	21
15.1	FUNDING SOURCE.....	21
15.2	COSTS TO THE PARTICIPANT.....	21
15.3	PARTICIPANT REIMBURSEMENTS OR PAYMENTS	21
16	STUDY ADMINISTRATION	22
16.1	STUDY LEADERSHIP	22
17	CONFLICT OF INTEREST POLICY	22
18	REFERENCES.....	22
19	ATTACHMENTS	XX

List of Abbreviations

BMI	Body Mass Index
BNP	Brain Natriuretic Peptide
BP	Blood Pressure
CBRD	Center for Biospecimen Research and Development
CDC	Center for Disease Control
CRP	C-reactive protein
CTSI	Clinical Translational Science Institute
EDTA	Ethylene diamine tetraacetic acid
EHR	Electronic Health Record
EPA	Environmental Protection Agency
GCP	Good clinical practices
GLP	Good Laboratory Practices
GMP	Good Manufacturing Practices
HEPA	High Efficiency Particulate Air
HIPAA	Health Insurance Portability and Accountability Act of 1996
ICAM-1	Intercellular Adhesion Molecule-1
ICMJE	International Committee of Medical Journal Editors
IL-6	Interleukin-6
IRB	Institutional Review Board
MCIT	Medical Center Information Technology
NCATS	National Center for Advancing Translational Science
NIH	National Institutes of Health
NYU	New York University
PAC	Portable Air Cleaner
PCSK9	Proprotein convertase subtilisin/kexin type 9
PHI	Protected Health Information
PI	Principle Investigator
PM	Particulate Matter
PM _{2.5}	Particulate Matter <2.5 µm in diameter
TNFα	Tumor Necrosis Factor-alpha
TP	Treating physician
TRB	Translational Research Building
VCAM-1	Vascular Cell Adhesion Molecule

[figure not shown]
Protocol Summary

Title	Cardiometabolic Biomarker improvements associated with reduction in air pollution exposure via home air filtration: a pilot trial.
Short Title	Cleaner air for better cardiac biomarkers
Brief Summary	
In this research, we will conduct a double-blind, sham-controlled, randomized trial to examine the impact on cardiometabolic biomarkers of air pollution exposure reduction using home portable air cleaners (PACs) in a cohort of current adult patients at NYU Langone Health. This study is funded by CTSI (NIH/NCATS UL1TR001445) with two primary aims and two secondary/exploratory aims. In Aim 1, we will evaluate associations with PAC use with a priori specified biomarker of inflammation, tumor necrosis factor alpha (TNFα). We will determine if 4 weeks of home air filtration with PACs compared to sham is associated with significant reductions in TNFα concentrations when measured before and after intervention. Blood samples will be collected from 44 study participants before and after 4 weeks of PAC use (true and sham) for biomarker concentration measurement. In Aim 2, we will determine if reductions in fine particulate matter (<2.5 μm in diameter, PM_{2.5}) as a continuous variable are associated with significant reductions TNFα concentrations over a four-week period. In Exploratory Aim 1, we will explore associations between PAC use and concentrations of cardiometabolic biomarkers using a targeted proteomic panel, the Olink Explore 384 Cardiometabolic panel, measured before and after 4 weeks of intervention. This will be a hypothesis-generating analysis to identify possible novel biomarkers and pathways that may have importance in the physiological responses and clinical outcomes associated with air pollution exposure. In Exploratory Aim 2, we will explore if biomarkers identified in Exploratory Aim 1 with significant reductions after 4 weeks of PAC partially mediate the association between reductions in PM_{2.5} and changes in daily home blood pressure (BP) measurements. Participants will be given home BP monitors to transmit de-identified daily morning BP measurements to a secure database during the 4 week intervention period. Changes in morning systolic (BP) will be analyzed as the outcome of interest, with changes in biomarker concentrations evaluated as a mediator of the relations between pollution reduction and changes in BP.

Objectives	
The primary objective of this research is to examine how PACs that reduce air pollution exposure affect cardiometabolic biomarkers and how those may mediate relationships with cardiovascular risk factors such as hypertension.
 
Specific Aim 1: To determine if 4 weeks of home air filtration with PACs compared to sham is associated with significant reductions in TNFα concentrations when measured before and after intervention.
 
Specific Aim 2: To determine if reductions in PM_{2.5} are associated with significant reductions TNFα concentrations over a four-week period.
 
Exploratory Aim 1: To identify novel biomarkers of the cardiometabolic effects of PM_{2.5} exposure with PAC use with a targeted proteomic panel, the Olink Explore 384 Cardiometabolic panel, measured before and after 4 weeks of intervention.
 
Exploratory Aim 2: To determine if novel biomarkers identified in Exploratory Aim 1 are mediators of the relationship between PAC use and home BP reductions after 4 weeks of PAC use.

Methodology	Randomized, double-blind, sham-controlled pilot study
Endpoint	
Aim 1 primary endpoint: Change in circulating concentration of TNFα
 
Aim 2 primary endpoint: Change in indoor PM_{2.5} concentration
 
Exploratory Aim 1 primary endpoint: Change in concentration of 384 circulating biomarkers associated with cardiometabolic risk
 
Exploratory Aim 2 primary endpoint: Change in average AM systolic blood pressure over study period

Study Duration	4 weeks
Participant Duration	Maximum: 4 weeks
Population	We will perform a randomized, double-blind, sham-controlled trial of continuous (24 hours/day) bedroom PAC use in an outpatient cohort English and Spanish speaking adults ≥ 18 years of age with stable hypertension (defined as no medication changes in prior 30 days, systolic BP < 160 mm Hg and either ≥ 130 mm Hg without antihypertensive medications, or diagnosis of hypertension in medical records). Per guidelines, this range is considered safe to monitor without changes in antihypertensive medications. Additional inclusion criteria require participants to measure home blood pressure twice daily, participate in video conference for home equipment setup, and ability to visit clinic for blood draws before and after the study period. Participants will be excluded if they are current smokers, currently have known coronary artery disease, have known systemic inflammatory conditions (such as rheumatoid arthritis, inflammatory bowel disease, cancer), or are currently taking any anti-inflammatory medications or medications that target inflammatory cytokines. We aim to enroll 44 participants, randomized in a 1:1 ratio to PAC with HEPA filtration versus sham filtration.

Study Sites	Participants will be consented and enrolled at NYU outpatient clinic facilities in Manhattan. At this visit, patients will have baseline blood drawn and will receive all study equipment. Participants will set up air pollution monitor and PAC in their homes with video chat guidance. PAC will be run continuously in participant bedrooms for 4 weeks. Participants will have follow-up visit to NYU Langone hospital clinical lab for post-intervention blood collection and equipment return.
Number of participants	To achieve 44 study participants, we will need to identify \approx 300 eligible participants from the electronic health record (EHR) in NYU clinics. There will be 22 participants per arm (sham versus active filtration).
Statistical Analysis	
For all Aims: descriptive summary statistics, such as mean and standard deviation (or median and inter quartile range) will be reported for continuous variables and counts and proportions for categorical variables. Graphical displays of all variables will be examined, with attention to assessing balance in these characteristics by intervention group, and with assessment of the distribution of variables, relevant to the choice of statistical tests. Statistical comparisons between the PAC and sham groups will be performed using a two-group two-sided t-test or nonparametric Wilcoxon test for continuous variables and Chi-square test for categorical variables. Distributions of biomarker concentrations will be examined and non-normally distributed concentrations will be log-transformed, as needed.
 
The analysis of our primary outcome for Aim 1 will use linear mixed-effects models with the change in prespecified biomarker, from pre-intervention to post-intervention, concentrations as the dependent variable and treatment arm as the independent variable. While randomization should obviate the need for additional adjustment, models will be adjusted for age, gender and BMI, as these are known to be related to inflammatory biomarker concentrations. These models use subject-specific random intercepts to account for heterogeneity between subjects and will account for within subject correlation between biomarker observations.
 
For Aim 2, we will also utilize similar models incorporating $PM_{2.5}$ as the independent variable. This will be assessed as the difference between pre-intervention baseline $PM_{2.5}$ concentration and the time-weighted average concentration of $PM_{2.5}$ from the 14-day intervention period.
 
For Exploratory Aim 1, we will evaluate the Olink panel results using mixed-effects models for the remaining biomarkers that were not prespecified. These will be the same models as for Aims 1 and 2, adjusted for age, gender, and BMI. For Exploratory Aim 2, we will evaluate associations of PAC use and $PM_{2.5}$ reduction with measured AM systolic blood pressure in this clinical cohort. We will perform mediation analysis using biomarkers with significant associations in Exploratory Aim 1 as mediators of the relations between $PM_{2.5}$ reduction and change in blood pressure.

Schematic of Study Design

1 Key Roles

Principal Investigator

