3.1 Primary Objective

The primary objective of this research is to examine the effectiveness of PAC use in improving inflammation related to cardiovascular disease.

Specific Aim 1: To determine if 4 weeks of home air filtration with PACs compared to sham is associated with significant reductions in TNF α concentrations when measured before and after intervention.

Specific Aim 2: To determine if reductions in PM $_{2.5}$ as a continuous variable are associated with significant reductions TNF α concentrations over a four-week period.

Exploratory Aim 1: To explore associations between PAC use and concentrations of cardiometabolic biomarkers using a targeted proteomic panel, the Olink Explore 384 Cardiometabolic panel, measured before and after 4 weeks of intervention.

Exploratory Aim 2: To explore if changes in TNF α and other novel cardiometabolic biomarkers partially mediate the effects of PACs on home blood pressure.

4 Study Design and Endpoints

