Exploratory Aim 2: To explore if changes in TNF α and other novel cardiometabolic biomarkers partially mediate the effects of PACs on home blood pressure. For this Aim, participants will monitor blood pressure daily during the 4-week intervention period using commercially available BP monitor with a paired data hub that transmits BP measurements to an online dashboard in real time. Participants will receive written and verbal instructions for proper BP recording technique at the baseline visit. They will record two measurements in a seated position each morning and evening during the study periods. The outcome of interest will be the mean of two AM systolic blood pressure measures. We will perform mediation analysis to analyze the direct and indirect effects of changes in significant biomarkers and PM_{2.5} changes on AM systolic BP. Based on our own pilot study of the effect of PAC use on AM systolic BP, we anticipate up to 30% missing BP measurements. We surveyed our prior pilot cohort regarding reasons for missing measurements and the predominant reported reason was forgetting; participants noted that they would have liked daily reminders. We will offer participants the option to receive daily text message reminders to record BP. These have been reported to be effective in other studies of home BP as well.

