4.2.2 Exploratory Endpoints

Exploratory Aim 1: The endpoints for Exploratory Aim 1 will be the % change in concentration of biomarkers from the Olink Explore Cardiometabolic panel over the 4-week intervention period calculated as:

$$\frac{([post - intervention] - [pre - intervention])}{[pre - intervention]} * 100\%$$

Exploratory Aim 2: The endpoint for Exploratory Aim 2 will be the change in AM systolic BP (mm Hg) as a function of the change in PM_{2.5} (in $\mu\text{g}/\text{m}^3$) from baseline.

5 Study Enrollment and Withdrawal

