7.6 Final Study Visit

Final Study Visit (Visit 2: 4 weeks after PAC turned on)

- Participants return study equipment: PM monitors, BP monitor data hubs, electricity monitors
- Collect blood for post-intervention biomarker measurement: <15 mL for all, additional ~10 mL for participants opting into future research.
- Final blood draw must occur ≤35 days from turning on PAC

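### Exploratory Aim 2 asks whether biomarkers mediate the effect of PAC use, but the pilot's mediation analysis takes non-randomised PM2.5 reduction as its exposure, and the blood pressure window is not fixed

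*Combined protocol and SAP*

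**What the plan says.** **The aim.** The Protocol Summary objectives ask whether biomarkers from Exploratory Aim 1 are "mediators of the relationship between PAC use and home BP reductions after 4 weeks of PAC use". Sections 3.1 and 4.1 ask whether TNFα and other biomarkers "partially mediate the effects of PACs on home blood pressure". The Brief Summary differs: there the biomarkers are to mediate the association of PM2.5 reduction with BP change.

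**The analysis.** The Protocol Summary, Statistical Analysis, says: "We will perform mediation analysis using biomarkers with significant associations in Exploratory Aim 1 as mediators of the relations between" PM2.5 reduction and BP change. Section 4.2.2 follows it: "The endpoint for Exploratory Aim 2 will be the change in AM systolic BP (mm Hg) as a function of the change in" PM2.5. Section 10.3 names PAC use as the exposure for mediation only in a secondary analysis within the larger R01 trial.

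**The outcome window.** The summary endpoint is "Change in average AM systolic blood pressure over study period". Section 4.1 says "The outcome of interest will be the mean of two AM systolic blood pressure measures" and names no day or week. Section 4.2.2 gives no window either.

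**The mediator.** Blood is drawn at baseline and once more at the final visit, where 7.6 says "Collect blood for post-intervention biomarker measurement".

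**The concern.** A mediation analysis has three paths: exposure to mediator, exposure to outcome, and mediator to outcome. When the exposure is the randomised arm, design protects the first two. When it is observed PM2.5 change, none is protected. PM2.5 change can also reflect outdoor air, season, household sources and how long the device actually ran, and some of these could bear on the biomarker or on BP. The mediation step names no confounders.

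The order of measurement adds a second difficulty. If BP is recorded before the biomarker is sampled, an association between them fits BP acting on the biomarker as well as the reverse.

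Section 10.3 says that the exploratory results should inform later cohorts and that the biomarker data will enter the R01 mediation analysis. A biomarker wrongly labelled a mediator here could carry forward.

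**Working it through.** The documents give no power or effect figure for the mediation analysis, so there is none to reproduce. The check sets the passages side by side and then uses an illustrative simulation.

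**1. Exposure, place by place**

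| Place | Exposure for mediation in the pilot |
|---|---|
| Protocol Summary, Objectives | PAC use |
| 3.1 | PAC use |
| 4.1, statement of the aim | PAC use |
| 4.1, analysis sentence | PM2.5 change |
| Brief Summary | PM2.5 reduction |
| Protocol Summary, Statistical Analysis | PM2.5 reduction |
| 4.2.2 | PM2.5 change |
| 10.3 | none for the pilot; PAC use within the R01 |

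The aim is worded by PAC use in three places and by PM2.5 in one. Every description of the pilot's mediation analysis uses PM2.5. Section 10.5.1 randomises arm, 1:1, and nothing else.

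**2. Timing**

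The PAC is switched on within 7 days of the baseline draw (7.5), and BP is recorded daily during the four weeks (4.1). The final draw may fall up to 35 days after switch-on, and the BP data hub is handed back at that visit (7.6). Essentially all transmitted BP readings therefore precede the second biomarker sample, whichever window is chosen.

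**3. Simulation with true mediated effect zero**

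All parameters are assumptions on a standardised scale. A is arm (0/1), U an unmeasured factor, and each e independent standard normal noise:

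- PM2.5 reduction: P = A + cU + √(1 − c²)·e
- BP change: Y = −0.8A − mU + e
- Biomarker change: M = rY − mU + e

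Mediation is declared when exposure→M and M→Y given exposure are both significant at two-sided 0.05. There were 4,000 runs at n = 44 and 300 at n = 2000.

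| Scenario | Exposure | Mean indirect effect, n = 44 | False mediation, n = 44 | False mediation, n = 2000 |
|---|---|---|---|---|
| c = m = r = 0 | arm | −0.001 | 0.2% | 0% |
| c = m = 0.3, r = 0 | PM2.5 | −0.004 | 0.6% | 72.7% |
| c = m = 0.5, r = 0 | PM2.5 | −0.026 | 3.2% | 99.7% |
| c = m = 0.5, r = 0 | arm | −0.002 | 1.0% | 5.3% |
| r = 0.5, c = m = 0 | arm | −0.157 | 17.6% | 100% |
| r = 1, c = m = 0 | arm | −0.402 | 46.1% | 100% |

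Hand checks, with a the exposure→M slope and b the M→Y slope given exposure:

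- PM2.5, c = m = 0.5: Var(P) = 0.25 + 1 = 1.25. Cov(M,P) = −0.25, so a = −0.25/1.25 = −0.20. Cov(Y,P) = −0.8 × 0.25 − 0.25 = −0.45. Then b = (0.25 − 0.25 × 0.45/1.25)/(1.25 − 0.25²/1.25) = 0.16/1.20 = 0.133, and ab = −0.027.
- Arm, same U: a = 0, so ab = 0. But b = 0.25/1.25 = 0.20 when the truth is 0. The product is clean only because arm does not move the biomarker here, so mediator-outcome confounding is still present.
- Reverse path, arm: a = −0.8r and b = r/(1 + r²). For r = 0.5, ab = −0.4 × 0.4 = −0.16. For r = 1, ab = −0.8 × 0.5 = −0.40.

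**4. What a final-week window would change**

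If the BP effect grew linearly over 28 days (assumption), the mean over days 1–28 would carry (406/28)/28 = 0.518 of the day-28 effect, and the mean over days 22–28 would carry 25/28 = 0.893. If the effect is immediate, the two are equal. With the 30% missing readings that 4.1 anticipates, spread evenly, usable mornings fall from 28 × 0.7 = 19.6 to 7 × 0.7 = 4.9. Days 22–28 still precede the final draw.

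**5. How many panel markers might reach this step**

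Under Holm over 369 markers (10.3), the smallest p-value must fall below 0.05/369 = 0.000136. With 22 per arm, 80% power at that level needs a standardised difference of about (3.82 + 0.84) × √(2/22) = 1.40.

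**The case against.** The PM2.5 exposure is deliberate. The Brief Summary words the aim that way, 4.2.2 and the analysis text follow it, and 4.1 explains that PM2.5 is studied as a continuous variable alongside arm. The Protocol Summary also relates PAC use to morning systolic BP, and 10.3 plans arm-based mediation in the R01. All of this stands, and it shows that the wording of the aim is inconsistent. It does not give the pilot an arm-based mediation model, which is what the aim asks for in the objectives, 3.1 and 4.1.

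A reader might go further and infer that the analysis cannot answer Exploratory Aim 2. The documents do not support that. One wording of the aim is in PM2.5 terms, the exploratory analyses are declared hypothesis-generating, and the arm is on record for a better-matched model.

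A reader might also infer that the plan commits to a four-week BP mean, or that a biomarker sampled at week four can have no bearing on BP in week one. The window is inconsistent, not fixed: averaging in the summary endpoint may mean only the paired morning readings. A pre-to-post change can also stand as a proxy for a response under continuous filtration. Late sampling leaves the order unestablished without making the result meaningless.

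Finally, the consequence is limited. No primary conclusion depends on this aim, and step 5 suggests that few or no panel markers may qualify. TNFα can still enter under 3.1 and 4.1.

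**Conclusion.** The point holds as a mismatch between aim and analysis. The aim, as most places state it, concerns the effect of PAC use, while the pilot's mediation analysis uses an exposure that was not randomised. That much is read from the text and needs no assumption.

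The size is modest at this sample size. Under the assumed confounding, PM2.5 as exposure biased the indirect effect by 0.004 to 0.026 SD at n = 44. The timing limit could matter more (0.16 to 0.40 SD), but only if BP acts on the biomarker, and neither a change of exposure nor a final-week window removes it. Only the direction of these results should carry weight. How much of the variation in PM2.5 change comes from arm cannot be stated, because the documents give no PM2.5 levels or spread.

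With arm as exposure, mediator-outcome confounding remains. Either model therefore supports association and not causal mediation.

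**What to change.** - In the synopsis, 4.2.2 and 10.3, make randomised arm the exposure in the main mediation model of the pilot, and bring the Brief Summary into line. Keep PM2.5 reduction as a secondary or sensitivity analysis. Its averaging period also needs settling, since 10.3 speaks of 14 days and the intervention lasts four weeks.
- State one BP window and use it in the aim, the endpoint, 4.1 and 4.2.2. A final-week mean may be added as a sensitivity analysis. It should not replace the full record on the ground of timing, because it cuts about 20 mornings to about 5 and does not restore the order.
- State two limits: essentially all BP readings precede the only post-baseline biomarker sample, and mediator-outcome confounding remains with arm as exposure. Describe results as associations.

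The cost is wording in a few sections and one further model. No new data, visits or samples are needed.

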We will also utilize similar models incorporating PM_{2.5} as the independent variable in place of PAC arm. This will be assessed as the difference between pre-intervention baseline PM_{2.5} concentration and the time-weighted average concentration of PM_{2.5} from the 14-day intervention period. For our exploratory aim we will evaluate the Olink panel results using mixed-effects models for the remaining biomarkers that were not prespecified. Additionally, we will explore associations of PAC use with measured blood pressure in this clinical cohort that likely differs from our current pilot cohort recruited from a community setting. Because this pilot will integrate with our larger R01 trial, for which blood pressure is the primary outcome of interest, we will incorporate this biomarker data into that trial for a secondary exploratory analysis of biomarkers as mediators in the association between PAC use and blood pressure reductions.

In our exploratory analysis, there will be multiple testing bias due to utilizing a panel of 369 possible biomarker outcomes. With this size pilot cohort, it will be unlikely to achieve statistical significance if strict adjustments for multiple testing are undertaken. However, we will use the Holm procedure to evaluate for significance. Overall, these exploratory analyses will be hypothesis-generating and can help inform the design and sample size of future cohorts.

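### The synopsis and the body of the protocol disagree on whether TNFα is a candidate mediator in Exploratory Aim 2, and also on which direction of change qualifies and which exposure is mediated

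*Combined protocol and SAP*

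**What the plan says.** TNFα is the biomarker fixed in advance: the Brief Summary in the Protocol Summary calls it the a priori "specified biomarker of inflammation, tumor necrosis factor alpha".

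The Statistical Analysis entry of the Protocol Summary says of Exploratory Aim 1 that "we will evaluate the Olink panel results using mixed-effects models for the remaining biomarkers that were not prespecified". For Exploratory Aim 2 it then says "We will perform mediation analysis using biomarkers with significant associations in Exploratory Aim 1 as mediators". The Brief Summary draws mediators from "biomarkers identified in Exploratory Aim 1 with significant reductions after 4 weeks of PAC". The Objectives entry puts the aim as "To determine if novel biomarkers identified in Exploratory Aim 1 are mediators of the relationship between PAC use and home BP reductions". Neither of these two statements of Exploratory Aim 2 names TNFα.

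Section 3.1 asks something different: whether changes in TNFα "and other novel cardiometabolic biomarkers partially mediate the effects of PACs on home blood pressure". Section 4.1 repeats that aim, and its method sentence plans mediation with changes in biomarkers that are significant, without confining them to Exploratory Aim 1.

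Section 10.3 keeps the synopsis restriction for the panel models, "using mixed-effects models for the remaining biomarkers that were not prespecified". It mentions mediation only as a secondary exploratory analysis within a larger trial, and gives no rule for choosing mediators.

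**The concern.** Section 2.1 closes its opening argument on the idea that TNFα may link particulate exposure to blood pressure, and TNFα is the only mediator named in Exploratory Aim 2 as the body states it. The synopsis is the only statistical-analysis text that says how mediators are chosen. An analyst who follows it literally would not estimate the TNFα pathway, and the aim in Sections 3.1 and 4.1 would go unanswered for its one named mediator. An analyst who follows Section 4.1 would estimate it only after a significant TNFα result. If the choice between these is made after the data are seen, the analysis is post hoc.

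Two further differences add to the ambiguity: whether a protein must fall to qualify, and whether the pathway starts at PAC arm or at PM2.5 reduction.

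**Working it through.** The point rests on comparing texts, so there is no figure in the plan to reproduce.

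| Place | Candidate mediators | TNFα | Direction | Exposure |
|---|---|---|---|---|
| Synopsis, Brief Summary | Exploratory Aim 1 findings | Not named; not expressly excluded | Reductions only | PM2.5 reduction |
| Synopsis, Objectives | Novel Exploratory Aim 1 findings | Not named; the word novel leans against it | Not stated | PAC use |
| Synopsis, Statistical Analysis | Exploratory Aim 1 findings among non-prespecified proteins | Omitted if read literally | Any association | PM2.5 reduction |
| Section 3.1 | TNFα and other novel biomarkers | Named | Not stated | PAC use |
| Section 4.1 | Biomarkers with significant changes | Named in the aim; admitted by the method if significant | Not stated | PAC use in the aim; PM2.5 change in the method |
| Section 4.2.2 | Not stated; the Exploratory Aim 1 endpoint covers panel biomarkers with no carve-out | Not excluded | Not stated | PM2.5 change |
| Section 10.3 | Biomarkers in general, in the larger trial | Not excluded from mediation | Not stated | PAC use |

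The exclusion in the third row takes three steps. TNFα is prespecified. Exploratory Aim 1 is modelled there on biomarkers that were not prespecified. Mediators come from Exploratory Aim 1. TNFα therefore falls outside the set whatever its p-value. Sections 3.1 and 4.1 cannot be reconciled with that.

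Some arithmetic shows how often a rule based on significance might yield a mediator. Section 10.4 gives no standard deviation or R², so this is context under stated assumptions: exactly 80% power with 66 analysed participants (33 per arm), a two-sided 0.05 test, a normal approximation, and no gain from covariates.

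- Implied standardised effect: d = (1.960 + 0.842) × √(2/33) = 0.690.
- Power at 22 per arm: Φ(0.690 × √(22/2) − 1.960) = Φ(0.327) ≈ 63%. With 10% dropout (19.8 per arm) it is about 58%.
- Section 10.4 assumes a 10% change, whereas Section 2.1 reports a pooled TNFα difference of 2%, not significant. With the same spread, d = 0.690/5 = 0.138, and power at 22 per arm is Φ(0.138 × √11 − 1.960) = Φ(−1.50) ≈ 7%.
- If significance for panel proteins means Holm significance over 369 proteins (Section 10.3), the first-step threshold is 0.05/369 = 0.000136. At d = 0.690 and 22 per arm, power per protein is Φ(2.287 − 3.816) ≈ 6%.

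On these assumptions the chance that TNFα qualifies under Section 4.1 ranges from roughly 7% to 63%. Section 10.4 claims more than 80% power at 66, so 63% would be somewhat higher if the margin is real.

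**The case against.** A reader of the synopsis might infer that TNFα can never be tested as a mediator, however strong its result. The documents do not support that. The Section 4.1 method is not limited to Exploratory Aim 1 or to non-prespecified proteins, so a significant TNFα result would qualify there. Sections 3.1, 4.1 and 4.2.2 define Exploratory Aim 1 over the panel without a carve-out, and Section 4.1 says TNFα is measured on that panel. The reference to remaining biomarkers may have been meant only to avoid repeating the Aim 1 model. Only the Statistical Analysis entry ties the mediator set to non-prespecified proteins; the Brief Summary and Objectives point the same way but do not contain that restriction.

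A reader might also infer that a planned, selection-free mediation estimate is being lost. None was planned: Section 4.1 itself conditions on significance. Nor is TNFα the only mechanism under study. Section 2.1 also discusses oxidative stress and sympathetic tone, and lists several other proteins for exploration.

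Finally, this is an exploratory aim in a pilot, and Section 10.3 calls the exploratory analyses hypothesis-generating. All of this stands and limits the point. It does not remove the conflict between the synopsis rule and the aim in the body.

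**Conclusion.** The point holds as an inconsistency. The literal synopsis rule omits TNFα, Sections 3.1 and 4.1 name it, and Section 4.1 admits it only if significant. The direction conflict within the synopsis and the split over exposure are also real. The reading of the synopsis depends on taking its reference to non-prespecified biomarkers at face value.

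The size is modest: no primary analysis, error rate or sample size is affected. What is at stake is whether the one mediator named in the body's version of the aim is estimated at all, and whether that is settled before unblinding. It is a cheap improvement and not a flaw that threatens the trial.

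**What to change.** State one mediator rule, in the same words, in the Brief Summary, Objectives and Statistical Analysis entries of the Protocol Summary and in Sections 4.1 and 10.3:

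- TNFα is the prespecified mediator for Exploratory Aim 2. Its indirect effect and confidence interval are estimated and reported whatever its Aim 1 p-value. This goes beyond the current Section 4.1, which must be amended as well.
- The exposure is named: PAC arm, PM2.5 reduction, or both. The Exploratory Aim 2 endpoint in Section 4.2.2 should agree with that choice.
- Panel proteins associated with the exposure in either direction are additional mediators, labelled data-selected and hypothesis-generating. The text should say whether significance here means after the Holm procedure.

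TNFα and home blood pressure are already in the planned data collection, so the cost is the wording and one extra exploratory model (two if both exposures are chosen). The downside is that the estimate will probably be imprecise with 44 participants, and the report should say so.
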